### Primary outcome analysis

The aim of the analysis is to answer the research question: did the Restorative Mentoring intervention (treatment) reduce post-treatment contact with the police compared to the Restorative Choices intervention (control)?

The primary outcome for this study is contact with the police, defined as the number of times the CYP appear in the police data as perpetrators, victims or for missing person episodes. These data will be taken from Greater Manchester Police administrative records.

Contact with the police is a discrete count variable starting at 0. These data will be collected one month before the trial ends, for a period 1 year prior to the recruitment date and for 3 months after completion of the intervention for all CYP.

It should be noted that the primary outcome, which is police contact with the CYP, is susceptible to biases in reporting and recording of crimes. These biases may stem from a number of factors, including characteristics of both the victim and the offender, such as ethnicity and gender. Nevertheless, we anticipate that the RCT design remains robust to these biases, as randomisation into the treatment and control groups is conducted independently of the police's reporting and recording of crimes.

There are two ways of analysing the data, depending on the distribution assumed for the dependent variable, which is total police contacts. As a discrete count random variable, it may be assumed to follow a Poisson or Negative Binomial distribution. However, if the mean of that distribution is far from 0, the Poisson and Negative Binomial distributions may be approximated by the continuous normal distribution. It is not clear a priori which distribution will be the better approximation, and therefore we consider below both scenarios. In any case, we do not expect major differences; the issue of whether a variable should be treated as continuous or discrete has received much attention in the randomized control trial literature and the main finding is that unless the outcome is binary or it is a "time to a first event", information will not be lost when treating a count variable as a continuous one, see, e.g. Herbison et al. (2015).

For the analysis, the headline estimate will be derived from an intention to treat effect (ITT), denoted by  $\beta$  in the regression:

$$g[E(Y_i|T_i)] = \alpha + \beta T_i,$$

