where  $Y_i$  is the primary outcome for individual  $i$ , and  $T_i$  is an indicator variable equal to 1 if person  $i$  was assigned to treatment and 0 if person  $i$  was assigned to the control group. The function  $g$  is the link function and is equal to the natural logarithm function if the dependent variable is assumed to be Poisson or Negative Binomial.

Hypothesis testing in the above regression complies with the power predictions of the study. The effect size will be measured by the Incidence Rate Ratio if the data are assumed to be Poisson or Negative Binomial, and by Cohen's  $d$  if they are assumed approximately normal. If the data are Poisson/Negative Binomially distributed, the necessary sample size to detect a "small" effect of at least 1.22, see e.g. Cohen (1992) and Olivier et al. (2017), with  $\alpha=0.05$  and

80% power is 322 CYP equally split between the treatment and control groups. Alternatively, if the data are assumed to be normally distributed, then to detect a “small” effect size of at least 0.3 is 352 CYP. Therefore, a sample of 352 CYP will lead to as sufficiently powered study irrespective of the data distributional assumption.

We will additionally estimate a regression with covariates:

$$g[E(Y_i|T_i, Z_i)] = \alpha + \beta T_i + Z_i' \gamma,$$

where  $Z_i$  is a vector of individual characteristics that are not affected by the intervention (sex, age, ethnicity, district, the number of contacts with the police in the year prior to referral, and referral source). The analysis below depends on the over-arching assumption that the sample of observations are independent to each other. This is reasonable as the sample is only a small subset of the whole population.

The dependent variable here is a count variable and it is highly likely that the lower values will have much higher frequency, in other words it is heavily skewed to the right. This feature of the data suggests that they are best analysed using Poisson regression. Mathematically, the Poisson regression takes the form:

$$Y_i | \lambda_i \sim Poi(\lambda_i)$$

where  $\lambda_i = \alpha + \beta T_i + Z_i' \gamma$ .

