An additional assumption that needs to hold for the Poisson regression is that conditionally on the regressors, the mean and variance of  $Y_i$  must be equal to each other. This is called equidispersion. If this assumption does not hold and the variance is greater than the mean, then we must estimate the model using the Negative Binomial regression, which is able to deal with what is called overdispersion.

The Negative Binomial regression works for the same type of data as the Poisson regression, however it also contains an additional term which captures the excess variance, as typically the variance is greater than the mean, when they are not equal. The Negative Binomial distribution is a Poisson-gamma mixture, where a gamma noise variable which has a mean of 1 and a scale parameter of  $\nu$  has been included resulting in the following distribution:

---

 This calculation is based on the average number of police contacts for the control group in the pilot study, which is 1.8. Given that the pilot study participants did not have a full six-month follow-up it is expected that in the efficacy study this average will be much higher. However, the higher the average, the fewer observations are necessary for the power calculations. Therefore, 322 observations is a conservative estimate given that even fewer may be required.

$$P(Y = y_i | \mu_i, a) = \frac{\Gamma(y_i + a^{-1})}{\Gamma(y_i + 1)\Gamma(a^{-1})} \left( \frac{a^{-1}}{a^{-1} + \mu_i} \right)^{a^{-1}} \left( \frac{\mu_i}{a^{-1} + \mu_i} \right)^{y_i}$$

Where  $\mu_i = t_i\mu$  and  $a = 1/v$ . The parameter  $\mu$  may be interpreted as the risk of a new occurrence of the event during a specified exposure period  $t$ .

If the dependent variable can be approximated by the continuous normal distribution, then the regression models above become linear and will be estimated by least squares. In this case, the coefficient  $\beta$  is numerically equal to the difference of means between the control and the treatment group.

Finally, as it is expected that compliance will not be perfect, the analysis will involve estimating a local average treatment effect (LATE), which will provide an estimate of the treatment effect for individuals who engage with the intervention ([Imbens & Angrist \(1994\)](#), [Imbens & Wooldridge \(2009\)](#)). In this case, treatment assignment will be used as an instrument for whether individuals get treated or not (see Compliance section).

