### **Presentation of outcomes**

The effect size will be reported based on the Incidence Rate Ratio or Cohen's  $d$  formulas. The incidence rate ratio (IRR) is given by:

---

 This means that the CYP is classified by REMEDI as a closed case, which indicates that the CYP has completed all the sessions (occasionally 1 or 2 sessions under or over the specified amount). While there is no agreed definition of compliance, we follow this strict definition after discussion with the intervention provider.

$$\text{IRR} = \exp(\hat{\beta}),$$

where  $\hat{\beta}$  is the maximum likelihood estimate from the Poisson and Negative Binomial distributions. The confidence interval is estimated by applying the delta method to the inverse of the estimated Fisher Information matrix.

Cohen's d is equal to the difference in the average of the variable in the treatment and control group divided by the standard deviation of the pooled sample:

Cohen's

$$d = \frac{\bar{Y}_t - \bar{Y}_c}{\text{s.e.}(Y)}$$

The confidence interval for d is given by

$$[d - 1.96 \times \sigma(d), d + 1.96 \times \sigma(d)]$$

where

$$\sigma(d) = \sqrt{\frac{N_1 + N_2}{N_1 N_2} + \frac{d^2}{2(N_1 + N_2)}}.$$

The t-tests and confidence interval formulas are based on the normal distribution as the sample size is expected to be large. These will be used to examine the statistical significance of the estimated coefficients. The formula for t-statistic is given by

$$t = \frac{\hat{\beta}}{\text{s.e.}(\hat{\beta})}.$$

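### On the Poisson/Negative Binomial route the IRR's standard error comes from the fitted model alone; if a few CYP hold a long tail of contacts it can be too small, and a robust standard error would guard against this at little cost

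*SAP*

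**What the plan says.** The primary outcome is one summed count, "defined as the number of times the CYP appear in the police data as perpetrators, victims or for missing person episodes" (SAP, Primary outcome analysis). The SAP's Introduction describes it differently, as contacts where the CYP is a suspect.

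On shape, the SAP says "it is highly likely that the lower values will have much higher frequency, in other words it is heavily skewed to the right". If the variance exceeds the mean, "then we must estimate the model using the Negative Binomial regression, which is able to deal with what is called overdispersion". No further step is given if NB also fits poorly.

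For the IRR, SAP, Presentation of outcomes states: "The confidence interval is estimated by applying the delta method to the inverse of the estimated Fisher Information matrix". The same section gives a t-statistic, the coefficient over its standard error, referred to the normal distribution. Of the t-tests and intervals it says "These will be used to examine the statistical significance of the estimated coefficients". It does not say where the standard error in the t formula comes from; the natural reading is the same information matrix.

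The only distributional figure is in a footnote: "This calculation is based on the average number of police contacts for the control group in the pilot study, which is 1.8". No variance, dispersion, maximum or split by contact type is given. Neither document mentions a robust standard error, bootstrap, permutation test, check of NB fit or rule for extreme counts. The SAP also allows a least-squares analysis with Cohen's d.

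**The concern.** The inverse Fisher information takes the model's variance as true: variance equal to the mean for Poisson, mean + a × mean² for NB. NB maximum likelihood estimates the dispersion a largely from the many low counts. If a small group of CYP holds a long tail, the fitted variance can fall below the real one.

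The outcome makes such a tail conceivable. Three kinds of contact are added together. The Protocol counts a re-arrest for the same offence once (Outcome measures, footnote), but states no similar rule for repeated missing-person episodes. What would be at stake is the width of the headline interval and the size of its test.

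**Working it through.** **The plan's own figures.** For d = 0.3, two-sided 5% and 80% power, the t-based formula gives 175.4, so 176 per arm and 352 in total, as stated. For the count model the SAP states an "effect of at least 1.22" and that the sample for "80% power is 322 CYP equally split between the treatment and control groups". The Poisson formula per arm is (zα + zβ)² × (1/λ₀ + 1/λ₁) / ln(IRR)², with λ₀ = 1.8 and λ₁ = 1.8 × 1.22 = 2.196:

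- one-sided 5%: 2 × 6.18 × 1.0109 / 0.03954 = 316, within 3% of 322;
- two-sided 5%: 2 × 7.85 × 1.0109 / 0.03954 = 401.

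The sidedness is a separate matter. What counts here is that the calculation contains a mean and no dispersion, so it says nothing about the tail.

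**Formulas.** With only the arm indicator in the model, each fitted arm mean equals the observed arm mean under Poisson and NB alike, so the IRR estimate does not depend on the choice. With n per arm and common mean μ:

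- NB, inverse Fisher: var(log IRR) = (2/n)(1/μ + a) = (2/n)(μ + aμ²)/μ²
- actual, which the sandwich estimates: var(log IRR) = (2/n)σ²/μ²

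The two agree only when σ² = μ + aμ².

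**One case by hand.** Assume 3% of CYP average 15 contacts, the rest are Poisson and the overall mean is 1.8.

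- Mean of the rest: (1.8 − 0.03 × 15)/0.97 = 1.392.
- True variance: 1.8 + 0.03 × 0.97 × (15 − 1.392)² = 7.19.
- The NB fits to such data gave a = 0.68 on average, so the fitted variance is 1.8 + 0.68 × 3.24 = 4.00.
- Fitted s.e.: √(2/176 × 4.00/3.24) = 0.1185. True s.e.: √(2/176 × 7.19/3.24) = 0.1588. Ratio: 0.746.
- Implied rejection rate: 2Φ(−1.96 × 0.746) = 14.4%. Simulated: 13.8%.

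The same steps for true NB data with dispersion 1 (average fitted a = 0.99) give variances of 5.01 and 5.04, a ratio of 0.997 and a rate of 5.1%. Simulated: 5.3%.

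**Simulated false-positive rates.** 176 per arm, mean 1.8, no effect, two-sided nominal 5%, unadjusted model. There were 1,200 to 3,000 trials per scenario, so the Monte Carlo s.e. at 5% is about 0.4 to 0.6 points. Every tail is an assumption.

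| Data | NB, inverse Fisher | Sandwich |
|---|---|---|
| NB, dispersion 0.5 / 1 / 2 | 5.6 / 5.3 / 5.0% | 5.7 / 5.2 / 5.1% |
| NB base, plus 5% of CYP averaging 6 extra contacts | 6–9% | 5–6% |
| NB base, plus 5% averaging 10, 3% averaging 12 or 8% averaging 9 extra; heavy group Poisson | 5–8% | 5–7% |
| Same three, heavy group gamma-Poisson (shape 2 or 1) | 10–16% | 6–7.5% |
| Poisson-lognormal, σ = 1 / 1.25 / 1.5 | 8 / 13 / 19% | 5 / 7 / 7.5% |
| 2% averaging 10 / 3% averaging 15 / 3% averaging 20 / 2% averaging 30; rest NB, dispersion 1 | 6 / 9 / 13 / 20% | 6 / 5 / 6 / 7% |
| Same four; rest Poisson | 7 / 14 / 20 / 29% | 5 / 6 / 6.5 / 8% |

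A second Poisson-lognormal run gave 9 to 17% with Fisher. In the worst case tried (2% averaging 30, heavy group itself overdispersed) the rates were 38% and 10%. The least-squares difference in means stayed at 4 to 6% in every scenario of the 3,000-trial run.

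**Cross-check** in standard software (400 trials each, Monte Carlo s.e. about 1.1 points), for three heavy-tail cases: Fisher 11 to 17%, sandwich 5 to 8%, permutation 3 to 7%. The NB standard error was 0.77 to 0.86 of the robust one.

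**The case against.** Much of the case against stands.

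- **The tail is not in the documents.** A share and an average for the heavy group do not fix the result. With an overdispersed base, the same three groups give 5 to 8% if their counts are Poisson around their mean and 10 to 16% if gamma-distributed. The three groups would hold 20 to 40% of all contacts (0.36/1.8, 0.5/1.8 and 0.72/1.8). The Protocol (Outcome measures, Primary outcome) points the other way, expecting referred CYP to have had only limited police contact.
- **A route that resists the problem is already planned.** The SAP allows least squares. The Protocol's Analysis section plans simple differences in means, and its Table 4 lists a t-test for the police data. This limits the point to the Poisson/NB route. It does not repair the IRR interval if that is the headline result.
- **The adjusted model was not simulated.** Prior-year contacts are a covariate there and may absorb some of the heterogeneity.
- **The sandwich is not exact.** It can run above 5% when a handful of counts dominate.

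A reader might infer that the count must truly follow a Poisson or NB distribution. That is too strong: the mean-variance relation is enough. A reader might also blame missing-person episodes in particular. The documents do not show that these cluster, the Introduction's suspect-only definition would exclude them, and the Poisson-lognormal rows show that ordinary heterogeneity can do the same.

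**Conclusion.** The point holds in conditional form. On the Poisson/NB route, the interval, and by natural reading the test, rest on a variance that the SAP does not check beyond the move from Poisson to NB. If NB fits, nothing is lost. If a small group holds a long tail, the standard error can be too small: about 4 to 9% false positives for mild tails or Poisson-type tails on an overdispersed base, about 10 to 17% for gamma tails or Poisson-lognormal heterogeneity, and more in extreme cases.

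These figures assume 176 per arm, a mean of 1.8, no true effect and the tails listed. It is tempting to conclude that this trial's p-value will be too optimistic or its error rate doubled. The documents do not support that, because they give no variance or upper tail. Nor is the IRR estimate biased by this. The lack of tail data is itself a reason to choose a standard error that does not depend on it. This is an inexpensive improvement to the SAP, not a flaw in the design.

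**What to change.** In SAP, Presentation of outcomes, state that the standard error of the coefficient, for both the interval and the t-statistic, comes from the heteroscedasticity-robust (sandwich) covariance, for Poisson and NB fits. This also covers a Poisson fit kept despite overdispersion (17, 24 and 36% false positives with Fisher at NB dispersion 0.5, 1 and 2). Add a permutation p-value for the unadjusted headline model, re-drawing arm labels under the trial's simple randomisation. Settle this before outcome data are seen, so that the choice of standard error cannot follow the result.

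The cost is a sentence or two in the SAP, one software option and a short permutation routine. If NB fits, the interval hardly changes. In three of the heavy-tail gamma scenarios the average standard errors were 0.193 against 0.166, 0.187 against 0.161 and 0.205 against 0.178, so intervals would be 15 to 16% wider. In the software cross-check they would be 16 to 30% wider (1/0.86 to 1/0.77). That extra width is uncertainty that the model-based interval would leave out.

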	
measure(s) (instrument, scale, source)
	
The first three scores are measured with the Strengths and Difficulties Questionnaire (SDQ). The remaining two scores (4 & 5) are measured with the Self-Reported Delinquency Scale (SRDS).
 
The SDQ and SRDS are completed by CYP at the point of consent, end of the intervention and 6 months after the end of the intervention as a follow-up (for CYP who start the interventions in the first 18 months of the trial).
 
For the SDQ CYP are asked to recall over the past 6 months, a period defined in the measure. For the SRDS, CYP are asked to recall over the past 3 months, this was a period defined for this study, in consultation with Remedi.
 
Scales are 0-20 for the internalizing and externalizing scores and 0-40 for the total difficulties score. Variety of delinquency ranges from 0-19 and volume of delinquency ranges from 0-198 (this excludes the scoring for Question 16, which is different from the other questions).
 
In the pilot study 73% of CYP consented into the interventions completed the initial questionnaires, and between one third and one half completed the end point questionnaires. We would expect these rates to be similar for this efficacy study and so could expect to receive around 257 initial questionnaires and 148 end point questionnaires. Six-month follow up questionnaires were not completed as planned during the pilot study and so we cannot use these completion rates to estimate the expected number of completed questionnaires during the efficacy study. However, we would expect completion rates to be lower than those at the end of the interventions, due to the break in contact with the CYP. As such we estimate between 10-20% of CYP will complete these questionnaires, which would equate to between 35-70 questionnaires. The expected attrition rate will affect the power of the analysis for these secondary outcomes.

Baseline for primary outcome
	
variable
	
The primary outcome of interest is the number of contacts of the CYP with the police, as perpetrators, victims or missing episodes.

	
measure (instrument, scale, source)
	
Police contact data will be taken from Greater Manchester Police administrative records for events 1 year prior to the intervention. Police contact data is a discrete count variable starting at 0.

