### Sample size calculations overview

	Protocol	Randomisation
Minimum Detectable Effect Size (MDES)	0.3	0.3
Alpha	0.05	0.05
Power	0.8	0.8

		Protocol	Randomisation
One-sided or two-sided?		Two-sided	Two-sided
Number of participants	intervention	176	176
	control	176	176
	total	352	352

The planned number of the trial participants is 352 CYP in its one year of implementation, 176 in the RM group and 176 in the RC group. The sample size is such that the trial is sufficiently powered to detect a Cohen’s d of at least 0.3 with probability 80%, which is in line with the funder guidelines and the previous literature.

The “simple” randomisation method will be used, which is a robust method against selection and accidental biases. We will use the statistical software package Matlab to implement the randomisation. Automated randomisation will ensure that the process is transparent and reproducible.

The above rest on the assumption that the alpha is equal to 0.05 and that the power is equal to 0.8. The minimum detectable effect size is equal to 0.3 as measured by Cohen’s d.

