### **Secondary outcome analysis**

In this part of the analysis, the aim is to answer the research question: did the Restorative Mentoring intervention (treatment) reduce difficulties and self-reported behaviour measures according to the SDQ and SRDS questionnaires, when compared to the Restorative Choices intervention (control). Furthermore, do these reductions differ by sex, ethnicity, and referral source.

The secondary outcomes for this analysis will include the CYP's emotional and behavioural difficulties and self-reported delinquency.

Emotional and behavioural difficulties are measured by the following three variables:

- 1) Internalizing score – measured on a scale from 0-20
- 2) Externalizing score – measured on a scale from 0-20
- 3) Total difficulties score – measured on a scale from 0-40

Self-reported delinquency is measured by:

4) Variety of delinquency - measured as the sum of the overall categories of delinquency  
Range: 0-19.

5) Volume of delinquency - measured as the sum of magnitudes of delinquency, over all  
categories Range: 0-198.

These variables will be compared across the treatment and control groups to test the null hypothesis of equal means against the two-sided alternative.

The regression analysis takes the form

$$Y_i = \alpha + \beta T_i + Z_i' \gamma + u_i \quad (2)$$

where  $Y_i$  is the secondary outcome for individual  $i$  (one of the aforementioned SDQ and SRDS variables).  $T_i$  is an indicator variable equal to 1 if  $i$  was assigned to treatment and 0 if  $i$  was assigned to the control group.  $Z_i$  is a vector of individual characteristics that are not affected by the intervention (sex, age, ethnicity, district, prior contact with the police, and referral source).  $u_i$  represents the random errors, which are not observed. Given that  $Y_i$  is a continuous variable we will employ a linear regression. The key assumptions that we will use is that the observations are independent to each other, there is mean independence  $E(u_i|T_i, Z_i) = 0$ , and that not all CYP have identical  $T_i$  and  $Z_i$  (no perfect multicollinearity). These assumptions are weak and easily satisfied.

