### **Subgroup analyses**

Given the potential for treatment to have different effects on individuals or specific groups, tests for heterogenous treatment effects will be performed to analyse whether individuals respond differently to treatment based on three observable characteristics: sex, ethnicity, and referral source. In this case, we will estimate the regressions specified above for subsamples based on these characteristics (male, female, white, non-white, police, youth services). Although the individual randomisation process was not stratified based on these

---

 The subgroup analysis will not be done in interactions of subgroups due to sample size limitations.

groups, if the sample size is sufficiently large to do a powered analysis, reporting results for groups defined post-randomisation could provide supplementary insights alongside the primary findings (Duflo et al. 2007). Therefore, this part of the analysis will also be exploratory, and we acknowledge potential limitations in terms of statistical power, since the sample size for each subgroup will be small.

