### **Longitudinal follow-up analyses**

One follow up point for measurement is specified – 6 months after the end of the intervention for the secondary outcomes. This will enable the estimation of potential longer lasting effects of the intervention by performing the same statistical analysis described above with data covering a longer period of time.

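### The SAP bases its t-tests and coefficient intervals on the normal distribution because the sample will be large, yet expects only 35–70 six-month forms; tests there have a true size of about 5.4–6.5%, not 5%

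*SAP*

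**What the plan says.** SAP, Presentation of outcomes: "The t-tests and confidence interval formulas are based on the normal distribution as the sample size is expected to be large". The section uses these formulas to judge the significance of the regression coefficients and sets no separate rule for follow-up or subgroup results.

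SAP, Design overview, on the six-month questionnaires: "As such we estimate between 10-20% of CYP will complete these questionnaires, which would equate to between 35-70 questionnaires". On the earlier time points, the trial "could expect to receive around 257 initial questionnaires and 148 end point questionnaires".

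SAP, Secondary outcome analysis: the SDQ and SRDS scores are first compared directly between arms "to test the null hypothesis of equal means against the two-sided alternative". They are then modelled by linear regression on arm plus age, sex, district, ethnicity, referral source and earlier police contact.

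SAP, Longitudinal follow-up analyses: longer-lasting effects are to be estimated by "performing the same statistical analysis described above with data covering a longer period of time".

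SAP, Subgroup analyses: "we will estimate the regressions specified above for subsamples based on these characteristics", meaning three binary splits by sex, ethnicity and referral source. Reporting is made conditional on adequate size, but no threshold and no expected subgroup sizes are given.

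**The concern.** The normal reference is justified by a premise that the same SAP contradicts for one of its planned analyses. When the error variance is estimated from few residual degrees of freedom, beta divided by its standard error follows a t distribution with heavier tails than the normal. A critical value of 1.96 then rejects a true null more often than 5%, and the interval for the coefficient is too short.

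The six-month forms are the trial's only planned evidence on lasting SDQ and SRDS effects. The error is largest where the data are thinnest, and it favours false positives.

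**Working it through.** **Inputs.** Total 352, d = 0.3, two-sided alpha 0.05, power 0.8 (SAP, Sample size calculations overview). Six-month return 10–20% (SAP, Design overview). End-of-intervention return 42% (Protocol, Secondary outcomes). Covariates as in the SAP's secondary regression. Ten local authority areas (Protocol, process evaluation, Research methods).

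**The plan's own figures reproduce.** A two-sample t calculation gives 175.4, so 176 per arm and 352 in total; the normal version gives 175 per arm, or 350. Returns: 352 × 0.10 = 35.2, 352 × 0.20 = 70.4, 352 × 0.42 = 147.8.

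**Assumptions.** Normal errors with equal variance. The documents do not give the covariate coding. I take district as nine dummies and ethnicity as binary, so the parameters are intercept 1 + arm 1 + sex 1 + age 1 + ethnicity 1 + district 9 + prior contact 1 + referral source 1 = 16.

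**Formulas.** True size of a nominal 5% test that uses 1.96 = 2·P(t_df > 1.96). Interval shortfall = 1 − 1.96 / t(0.975, df). Degrees of freedom are N − 2 unadjusted and N − 16 adjusted.

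| Analysis | N | df | True size | t(0.975) | Interval too narrow by |
|---|---|---|---|---|---|
| Six months, unadjusted | 35 | 33 | 5.85% | 2.035 | 3.7% |
| Six months, unadjusted | 70 | 68 | 5.4% | 1.995 | 1.8% |
| Six months, adjusted | 35 | 19 | 6.5% | 2.093 | 6.4% |
| Six months, adjusted | 70 | 54 | 5.5% | 2.005 | 2.2% |
| End of intervention, adjusted | 148 | 132 | 5.2% | 1.978 | 0.9% |
| Full sample, linear model, unadjusted | 352 | 350 | 5.1% | 1.967 | 0.3% |

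With a five-level ethnicity variable (19 parameters), the adjusted figures at 35 forms become 6.8% and 7.5%.

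**Where size passes 10%.** At df 6 it is 9.8%; at df 5 it is 10.7%. So five or fewer residual degrees of freedom are needed. In a subgroup of m forms the splitting variable drops out, which leaves m − 15 adjusted or m − 2 unadjusted.

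- Adjusted, all ten districts present: 18 forms (df 3) 14.5%; 20 forms (df 5) 10.7%; 21 forms 9.8%; 28 forms 7.2%; 35 forms 6.4%. So 16–20 forms exceed 10%, and with 15 or fewer the fit leaves no residual degrees of freedom.
- Unadjusted: above 10% only with 7 or fewer forms; 10 forms 8.6%; 14 forms 7.4%; 18 forms 6.8%.
- Subgroups of the primary outcome, at 10–50% of 352 and treated as linear: 5.2–6.4%.

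**The Cohen's d interval.** I checked separately the interval that the SAP writes out for d with 1.96. In simulation (200,000 runs per case) its coverage is about 94.9% at N = 35 and N = 70 with the within-group standard deviation, and about 95.4–96.4% with the total-sample standard deviation. It is not materially too narrow.

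**The case against.** The strongest reply is that the SAP has already discounted these results. It calls the secondary and subgroup analyses exploratory, warns of low power, and ties subgroup reporting to adequate size. That limits the consequences but does not remove the defect. A low-power warning concerns missed effects, whereas this error creates spurious ones, and none of the caveats mentions the reference distribution.

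The second reply is that the effect is small, and this stands. On the whole six-month sample the excess over 5% is between 0.4 and 1.5 percentage points.

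A reader might infer something stronger: that small-subgroup tests generally reject at more than twice the nominal rate. The documents do not support that. It needs five or fewer residual degrees of freedom, and neither subgroup sizes nor the coding of district is stated. Six-month subgroup regressions are themselves an inference from the longitudinal section's reference back to the earlier analyses. At 35 forms the smaller half of any binary split has at most 17, so a fully adjusted fit with all ten districts present would exceed 10% or leave nothing to test with. At 70 forms most plausible splits stay below 10%. It would also be wrong to attach the adjusted-model rates to the null of equal means, which the SAP states for the direct comparison of arms; that comparison has N − 2 degrees of freedom.

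A reader might also want t quantiles in the Cohen's d interval. That does not follow: its coverage is already close to 95%, and d is a raw two-group contrast to which regression residual degrees of freedom do not apply.

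Finally, the number of district dummies is a question of over-parameterisation, distinct from the reference distribution. That is fair, but the dummies are what drive the residual degrees of freedom so low.

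**Conclusion.** The point holds at modest size. The large-sample justification fails for the six-month analysis on the SAP's own expected numbers, and tests and intervals for mean differences and linear-model coefficients are mildly anti-conservative there. The unadjusted results need only the expected 35–70 forms and normal, equal-variance errors. The adjusted results also rest on the assumed 16 parameters. Rates above 10% are a corner case that the documents neither establish nor exclude. The main conclusions of the trial do not depend on this; it is worth correcting because the premise is wrong and the remedy is almost free.

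**What to change.** In SAP, Presentation of outcomes, state that tests and confidence intervals for mean differences and linear-model coefficients use the t distribution on residual degrees of freedom. Under normal errors this restores the 5% size. Leave the Cohen's d interval unchanged.

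For the six-month and subgroup linear models, either omit the district dummies, or set a minimum residual degrees of freedom in advance and report any fit below it descriptively.

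The cost is one or two sentences; t-based inference is standard software output. Exploratory intervals become slightly wider and, if district is dropped, those models lose that adjustment.
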